2.2.2 To identify signatures which are associated with LC stage

2.2.3 To identify signatures which are impacted by patient's pulmonary function status

3.0 Study Population

3.1 Inclusion Criteria

3.1.1 Male and female patients age ≥ 18 years, of all racial and ethnic origins, with suspected NSCLC stages I, II, and III, as evident through radiographic evidence and felt acceptable to undergo surgical resection.

3.1.2 Patients who have the ability to understand and the willingness to sign a written consent form.

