4.2 Experimental or Data Collection Methods

4.2.1 Clinical data collection:

All patients will be recruited within the Wake Forest Medical Center.

Medical history will be obtained from the patients charts to identify demographics (age, race, ethnicity, zip code), oncologic history (date of diagnosis and cancer type), and medical history of disease. Pulmonary function tests (PFTs) will be performed by Wake Forest Baptist Health Pulmonary Function Lab as a standard of care for pre-surgical assessment. PFTs will be accepted from other certified laboratories within six months of their appointment. Pulmonary function is

Pilot Study: Metabolic and microbial profiling of lung cancer
Wake Forest Baptist Comprehensive Cancer Center (WFBCCC)
WFBCCC # 03219

defined by undergoing standard pulmonary function studies per American Thoracic Society recommendations. The collection of these pulmonary function studies is often done as part of the pre-surgical assessment collected by a cardiothoracic surgical team. Also, the collection of pulmonary functions studies can help with the classification and treatment of underlying obstructive lung disease that can be crucial to post-operative management.

At pre- and post- surgery, the research nurse will obtain current medications, food/ingestion survey and tobacco use information. This information will be necessary to identify any exogenous factors confounding both metabolic and microbial signatures. Following surgery, information from the patient's final pathology report will be obtained to provide information on the tumor site location, characteristics of the cancer removed, and stage of the cancer.

4.2.2 Non-invasive sample collections:

Pre-surgery follow-up collection: During the patient's surgery consultation meeting with [name], Upon entering the are the patient will be given a receptacle for collection of a urine specimen. Given that blood collection may be seen as invasive to the patient, the patient will be prompted for a blood sample. If the patient agrees, the research nurse will collect 1 redtop vacutainer serum tube and 1 purple top blood tube from the patient. We will then initiate the saliva and exhaled breath volatiles (EBV) and

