6.0 Analytic Plan

6.1 Sample Size and Power

This is a pilot study therefore; many of the objectives are exploratory in nature. With this in mind, we plan to recruit two cohorts of patients with this study, 45 female and 45 males. In order to be able to examine the questions concerning the possible relationships of metabolic and microbial signatures over time and with lung cancer outcomes, both pre- and post- surgery measures are needed. Therefore, each patient must provide both a pre- and post-surgery sample (optional blood will be allowed) in order to be used in the signature analyses. If a post collection is not performed or collection is unsatisfactory, the patient will be replaced. Therefore, our target sample size of 90 patients (45 male/45 female) is the target for patients with both pre- and post- samples collected.

Pilot Study: Metabolic and microbial profiling of lung cancer
Wake Forest Baptist Comprehensive Cancer Center (WFBCCC)
WFBCCC # 03219

First, for the primary objective of assessing feasibility, we can determine the total number of patients needed in order to enroll 90 patients. To examine this question we will determine 1) the number of patients screened for the trial, 2) among those screened, the number who are eligible, 3) among those eligible, the number who consent to participate, 4) among those who participate, the number who provide pre-surgery samples, and 5) among those who provide pre-surgery samples, the number who provide post-surgery samples. Based on our design we will enroll patients until 90 provide pre- and post- surgery samples.

Since we do not know prospectively how many patients will be needed to enroll 90 we will conservatively estimate several possible scenarios and for each scenario describe the width of the corresponding 95% Exact Clopper Pearson confidence interval for proportions.

The table below shows different total number of patients needed to enroll 90 for the study, beginning with 120 (75% enrollment rate) to 180 (50% enrollment rate).

# screened and eligible	Number enrolled	Enrollment rate	Lower 95% limit	Upper 95% limit
120	90	75%	0.66	0.82
150	90	60%	0.52	0.68
180	90	50%	0.42	0.58

As can be seen from the above, the confidence intervals for each scenario are approximately +/- 10% or less depending on the scenario observed.

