For the other primary outcomes, metabolic and microbial assessments taken at two time points (pre- and post- surgery), we can determine statistical power in several ways. One straight-forward approach will be to assess the difference in biomarkers (metabolic or microbial) that can be detected when comparing pre- and post- surgical assessments within patients. If there are 90 patients then there is 80% power (using an alpha=0.05, 2-sided) to detect a difference in a biomarker measure equal to 0.30 standard deviations for that marker.

Since this is a pilot study, the above power calculations suggest that useful data concerning feasibility and effect size assessments for biomarkers can be determined in this study. Multiple comparison adjustments are not considered at this time since the focus of examining these effect size estimates is to determine an overall ranking of measures, in order to inform future studies concerning which signatures may be most promising to examine further.

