6.3 Analysis of Secondary Outcomes

For the analysis of metabolic and microbial measures we will examine each marker assessed both at pre- and post- surgery. We hypothesize that markers that are associated with lung cancer will change between the pre- and post- surgery setting, whereas markers that are independent of lung cancer will not change between the two time points. Therefore, a first analysis will be to examine

Pilot Study: Metabolic and microbial profiling of lung cancer
Wake Forest Baptist Comprehensive Cancer Center (WFBCCC)
WFBCCC # 03219

a series of paired t-tests to determine which markers significantly change between the two time points for patients.

In addition to this analysis, we wish to determine whether there are any marker signatures that appear in groups of patients. To do this we will use cluster analysis methods to determine whether there are any groups of patients who share similar marker profiles pre-, post- or change from pre- to post- for metabolic and microbial measures. If we are able to identify clusters of patients with common marker signatures, we will then determine whether there are other disease characteristics that are shared by these patients (i.e., tumor stage, lung function, etc.). This analysis approach will also be used below to address the analysis of secondary outcomes. As stated above, this is a pilot study, therefore these cluster analyses will be considered exploratory and hypothesis generating.

To address the two secondary objectives, we will use the same data gathered for the primary objective as described above, however we will compare those data to the two secondary outcomes measures (LC Stage and patient pulmonary function). The analytic difference between these two measures is that LC stage will be an ordinal variable and pulmonary function is a continuous measure.

For LC Stage, we will examine whether pre-surgery, post-surgery or change from pre- to post-surgery metabolic or microbial measures are different depending on LC Stage. To do this we can consider the metabolic or microbial measures as outcomes and use a general linear models framework to see if LC Stage (included as a class variable, but then examined as an ordinal variable using a contrast statement in GLM) is associated with any marker.

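### Section 6.3 reads pre/post change as association with lung cancer, but final pathology does not define who enters the paired t-tests, so any resection that proves not to be lung cancer would be included and could dilute cancer-specific changes.

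*Combined protocol and SAP*

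**What the plan says.** - **Entry.** Section 3.1.1 admits patients "with suspected NSCLC stages I, II, and III, as evident through radiographic evidence". The Appendix A checklist repeats this. No criterion requires histology.
- **Analysis set.** Section 6.1 makes a pre- and a post-surgery sample the condition for use in the signature analyses. It replaces a patient only when the post-surgery collection is missing or a collection is unsatisfactory. The target is counted the same way: "we will enroll patients until 90 provide pre- and post- surgery samples".
- **Pathology.** Under Section 4.2.1 the "final pathology report will be obtained to provide information on the tumor site location, characteristics of the cancer removed, and stage of the cancer". No section uses it to decide who enters the t-tests.
- **Test and reading.** Section 6.3 plans "a series of paired t-tests to determine which markers significantly change between the two time points for patients", on the hypothesis that "markers that are associated with lung cancer will change between the pre- and post- surgery setting" while unrelated markers stay the same.
- **Power and purpose.** Section 6.1 states: "If there are 90 patients then there is 80% power (using an alpha=0.05, 2-sided", for a difference of 0.30 standard deviations. It adds that "the focus of examining these effect size estimates is to determine an overall ranking of measures", to guide future studies. Objective 2.2.1 is to find which signatures indicate LC.

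**The concern.** Reading a pre/post change as LC-related presupposes that LC was removed. A patient whose lesion proves benign, or is another malignancy, had no LC removed but would still count in the mean change if both samples were given. If such patients show less LC-related change than the others, the average for an LC-specific marker is pulled toward zero. A change caused by the operation itself is not pulled down, because every patient had the operation. LC-specific markers could then drop in the ranking relative to surgery-driven ones, which runs against the use that Section 6.1 gives to the effect sizes. The 80% power figure would also describe an LC-specific change of 0.30 SD only if every pair came from an LC patient.

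**Working it through.** **Inputs from the plan (6.1, 6.3).** 90 pairs, paired t-test, two-sided alpha 0.05, change 0.30 SD. The SD is read as that of the within-patient difference and set to 1.

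**Assumed, because the documents give neither.** f, the share of pairs not confirmed as LC: 5, 10, 20%. k, the fraction of the LC change that those patients show: 0 (worst case) or 0.5.

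**1. Reproduce the plan's figure.** Noncentrality 0.30 × √90 = 2.846 on 89 degrees of freedom gives power 80.4%. The stated 80% is right if all 90 pairs carry the change.

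**2. Keep all 90 pairs.**
- Mean change = 0.30 × [1 − f(1−k)]
- Variance = 1 + f(1−f) × [0.30(1−k)]²
- Bias = 0.30 × f(1−k)
- Root-mean-square error (RMSE) = √(bias² + variance/90)

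Example, f = 10%, k = 0: the mean is 0.27 and the variance 1 + 0.09 × 0.09 = 1.0081. The standardized change is 0.27/√1.0081 = 0.269, and power is 71.3%. RMSE = √(0.03² + 1.0081/90) = 0.110.

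**3. Restrict to confirmed LC, without replacement.** n = 85/81/72 (5, 9 or 18 of 90 removed). The mean is 0.30, there is no bias, and RMSE = 1/√n. For n = 81, RMSE = 1/9 = 0.111.

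**4. Results for a true LC change of 0.30 SD.**

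| f | Restricted: n, power, RMSE | Pooled, k = 0: mean, power, RMSE | Pooled, k = 0.5: mean, power, RMSE |
|---|---|---|---|
| 5% | 85, 78%, 0.108 | 0.285, 76%, 0.107 | 0.2925, 78%, 0.106 |
| 10% | 81, 76%, 0.111 | 0.270, 71%, 0.110 | 0.285, 76%, 0.107 |
| 20% | 72, 71%, 0.118 | 0.240, 61%, 0.122 | 0.270, 72%, 0.110 |

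At f = 5% the expected number confirmed is 85.5. Using 86 instead of 85 gives 78.5% restricted power, so the comparison does not change materially.

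A simulation of the worst case (100,000 replicates; 5/9/18 non-confirmed of 90) agrees: pooled power 75.6/71.4/61.1%, restricted 78.1/76.0/71.0%.

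**5. Break-even.** Setting the two RMSE formulas equal and solving for the LC change shows how large it must be before restriction lowers RMSE: about 0.46/0.34/0.26 SD for k = 0, and 0.93/0.67/0.52 SD for k = 0.5.

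**6. A very small share.** At f = 2%, k = 0, power is 78.7% pooled against 79.5% restricted (n = 88), a negligible difference.

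**The case against.** The strongest reply is that the harm is conditional and may be small.

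- **The share is unknown.** This stands. The background (Section 1.0) says that one in four screened patients had incidental lung abnormalities, and a reader might take that for f. It describes CT screening findings, not resections. Section 4.2.1 records date of diagnosis and cancer type from the chart, and Appendix B has fields for primary diagnosis and its date, so some patients may already be diagnosed at entry.
- **Restriction need not improve accuracy.** This stands. The worst-case bias at f = 5–10% (0.015–0.030 SD) is well below the standard error of about 1/√90 = 0.105 SD. RMSE at 0.30 SD is then slightly higher restricted, even with k = 0. With k = 0.5 it is higher at all three values of f. Nothing in the documents fixes k at zero, and another resected malignancy could also move markers.
- **The stage model already uses pathology.** Partly. Section 6.3 also models change by LC stage, and a patient without LC would have no LC stage. That is a separate analysis and does not set the population for the overall t-tests.
- **All pairs is a legitimate population.** This stands for outcome 5.2.1, which asks what stays similar or changes between visits. It does not settle objective 2.2.1, which asks about LC.
- **Surgery remains confounded with tumour removal.** This stands. Restriction does not cure it.
- **This is an exploratory pilot.** True, and it limits the weight of the point. The marker ranking is still a stated product of this analysis, so its population should be stated. Otherwise the choice could be made after unadjusted results are seen.

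**Conclusion.** The omission is in the text: the stated conditions are paired samples, no diagnostic condition is added, and change is read as LC association. Followed as written, the plan would pool any non-LC resection into an estimate meant to indicate LC. If those patients show between none and all of the LC-related change, the estimate shrinks by at most the factor (1−f).

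The size rests on assumed f and k. At f = 5/10/20%, restriction adds roughly 2/5/10 points of power for 0.30 SD if non-confirmed patients show no LC-related change, and none if they show half. The dependable gain is less bias and an estimate that matches objective 2.2.1.

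A reader might infer more than the documents support:

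- That dilution will certainly occur. No rate of non-LC resections is given.
- That restriction always gains power or accuracy. The k = 0.5 figures show otherwise.
- That the clustering is harmed too. Section 6.3 forms clusters first and only then plans to "determine whether there are other disease characteristics that are shared by these patients", so diagnosis can be compared at that step.
- That feasibility or the order among LC-specific markers is affected. Feasibility does not use these tests, and a common factor (1−f) leaves that order unchanged.

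This is a worthwhile clarification of a secondary analysis, at the level of a change the sponsor could make.

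**What to change.** In Section 6.3:

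- For objective 2.2.1, run the paired t-tests in patients with both samples and pathology-confirmed lung cancer. Name the target diagnosis: NSCLC stage I–III, as suspected at entry under 3.1.1, or any primary lung cancer, which the wording of 2.2.1 would allow.
- Report the all-pairs t-tests alongside, as the answer to outcome 5.2.1.
- Report how many patients are confirmed, and describe the others separately, with benign lesions apart from other malignancies.

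In Section 6.1, state that 80% power for 0.30 SD applies to LC-specific changes only if all 90 pairs are confirmed.

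The cost is wording, since the pathology report is already collected and has its own form (Section 7.0). The downside is a smaller n in the LC-specific tests (about 85/81/72 at the assumed f) and possibly a slightly larger RMSE. The all-pairs tests keep the full 90 in view. Recruitment, replacement, the 90-pair target, the feasibility analysis and the clustering stay as they are.

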Biofluid and tissue microbiome analysis: DNA will be extracted from each blood, saliva and lung tumor tissue sample using the QIAamp® UCP Pathogen Mini Kit (Qiagen) with extended homogenization of the tissue samples using the Mini-Beadbeater-96 cell disrupter (Biospec Products). The quantity and quality of the DNA extracts will be determined using a DeNovix DS-11 FX+ Spectrophotometer/Fluorometer and Agilent 4200 TapeStation, respectively. The DNA will then be prepared for shotgun metagenomic sequencing using the Nextera® DNA Flex Library Preparation Kit (Illumina). DNA libraries will be normalized and quantified prior to pooling to ensure equal library representation. Pooled DNA libraries will then be sequenced using the Illumina NovaSeq 6000 S1 Reagent Kit and sequencer, generating 2 x 150 bp paired-end reads. Raw sequence reads (FASTQ files) will be imported into the Microbial Genomics Pro Suite within the CLC Genomics Workbench (version 11.0.1; <https://www.qiagenbioinformatics.com>) for QC, adapter trimming, and analysis. High-quality ($\geq Q30$) reads for each sample will be aligned to those in a blank extraction sample (negative control) that will be processed from DNA extraction through library preparation to identify and remove contaminating sequences. The filtered reads will then be aligned to a reference database consisting of complete genomes in the RefSeq database for prokaryotes (bacteria and archaea), eukaryotes (fungi and protozoa) and viruses for taxonomic profiling. The filtered reads will also be assembled into contigs *de novo*, and MetaGeneMark (20) will be used to identify protein-coding regions within the reads to predict functional diversity of the microbiota identified in the samples. The coding regions will be annotated with Pfam domains

Pilot Study: Metabolic and microbial profiling of lung cancer
Wake Forest Baptist Comprehensive Cancer Center (WFBCCC)
WFBCCC # 03219

and GO terms, and the abundance of functional categories will be estimated to build a functional profile for each sample.

The results from the taxonomic and functional profiling will each be merged to estimate similarities and differences among the samples. Heat maps will be generated using Euclidean distance and clustering based on average linkage to assess functional similarities between samples, and principal component analysis (PCA) ordination of Bray-Curtis similarity between samples will be used to visualize the microbiota diversity across the samples.

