In addition to this analysis where individual markers are considered separately, we will use cluster analyses (as described above) based on the marker data and then determine whether there are associations between cluster membership and LC Stage using 2-way contingency tables.

For pulmonary function, we will use the same approach as for LC Stage, except that pulmonary function will be considered as a continuous variable in the model. Thus, we can examine associations (correlations) between the marker measures and pulmonary function. In addition, pulmonary function can be examined at both time-points (pre- and post- surgery) thus we can examine the relationships between pulmonary function measures and biomarker measures at each time points (and the change in measures over time).

In addition to these analyses, additional exploratory analyses will be examined to determine whether other patient level characteristics (i.e., gender, age, smoking history (current/former/never), etc.) are associated with different metabolic and/or microbial signatures or measures in a general linear model framework.

Since this is a pilot study and the sample size is moderate ($n=90$), these additional analyses will be primarily hypothesis generating to allow us to determine whether there are potential signals in the data that may need to be further examined in larger trials.

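### Section 6.3 links multi-marker profiles to LC stage only through cluster membership, an insensitive route if the relation is graded; a test on the uncut profile should stand beside it

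*Combined protocol and SAP*

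**What the plan says.** Objective 2.2.2 is "To identify signatures which are associated with LC stage"; objective 2.2.3 asks the same for pulmonary function. Section 6.3 pursues these at two levels.

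- **Single markers.** Each marker is a continuous outcome in a general linear model. LC stage enters as a class variable and is then examined with an ordinal contrast. Pulmonary function enters as a continuous variable.
- **Several markers together.** Patients are clustered on their pre-surgery, post-surgery or change profiles. For stage, "we will use cluster analyses (as described above) based on the marker data and then determine whether there are associations between cluster membership" and stage, using two-way tables. The general paragraph on clustering is conditional: "If we are able to identify clusters of patients with common marker signatures, we will then determine whether there are other disease characteristics" that those patients share, with stage and lung function as examples. The pulmonary function paragraph says that it follows the stage approach, but spells out only continuous models and correlations.

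Section 6.3 gives no clustering method, no number of clusters and no whole-profile test. It labels the cluster analyses exploratory. In Section 4.2.2, the metabolomics paragraphs mention multivariate analysis without specifying it or tying it to stage or lung function. The microbiome paragraph says "Heat maps will be generated using Euclidean distance and clustering based on average linkage to assess functional similarities between samples", and uses Bray-Curtis similarity for an ordination plot; both are descriptive.

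**The concern.** Unsupervised clusters follow whatever dominates the variance between patients. Section 6.3 itself lists gender, age and smoking history as possible correlates of signatures, and Section 4.2.1 expects medication, food and tobacco to confound them. A stage effect that is graded and spread over many markers need not coincide with those divisions, so clusters can be almost unrelated to stage although the profile is related to it.

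The cut also has a cost when it falls in the right direction, because membership in two to four groups carries less information than a continuous score. In the stage table, the ordering that the single-marker contrast uses is dropped as well.

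At stake is the quality of the signature-level answer to two of the three secondary objectives, in a pilot meant to show which signatures deserve further study.

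**Working it through.** **Inputs from the documents.** Section 6.1: "our target sample size of 90 patients (45 male/45 female) is the target for patients with both pre- and post- samples collected"; "there is 80% power (using an alpha=0.05, 2-sided") "to detect a difference in a biomarker measure equal to 0.30 standard deviations for that marker"; and "Multiple comparison adjustments are not considered at this time". Stage mix, effect sizes, marker correlation, clustering method and number of clusters k are not given. Everything from step 2 on therefore rests on assumptions.

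**1. The plan's own figure.** Paired comparison: noncentrality 0.30 × √90 = 2.846. Normal approximation: Φ(2.846 − 1.960) = 81.2%. Noncentral t with 89 df: 80.4%. The stated 80% reproduces. It concerns one marker; no power is stated for the cluster step.

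**2. Cost of cutting one normal score.** Optimal cuts into k = 2, 3, 4 groups keep 64%, 81%, 88% of the variance. A linear relation with 80% power on the full scale has noncentrality (1.960 + 0.842)² = 7.85. After the cut, tested with k − 1 df:

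- k=2: 7.85 × 0.637 = 5.00, 1 df, power 61%
- k=3: 7.85 × 0.810 = 6.36, 2 df, power 61%
- k=4: 7.85 × 0.883 = 6.93, 3 df, power 58%

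The loss is 19 to 22 points.

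**3. One axis against stage.** Assume stages I/II/III at 50/25/25%, scores 0, 1, 2, and a shift of 0.36 SD per stage. Score variance = (0.25×1 + 0.25×4) − 0.75² = 0.6875. Noncentrality = 0.36 × √(0.6875 × 90) = 2.83.

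- Full-scale trend: Φ(2.83 − 1.96) = 81% (simulated 79%)
- Trend after a median split: Φ(2.83 × √0.637 − 1.96) = 62% (simulated 60%)
- Two-way table, 2 df, noncentrality 2.83² × 0.637 = 5.11: 51% (simulated 49%)

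The split costs about 19 points, and ignoring stage order about 11 more: some 30 in all.

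**4. Many markers, n=90, alpha 0.05, simulated.** The uncut profile is tested with a distance-based permutation test. Clusters are k-means with a chi-square table for stage, or ANOVA for pulmonary function (PF). Rows A use a 50/25/25 stage mix, a trend test on the uncut profile and k=2 or 3, with ranges over repeated runs. Rows B use 60/20/20 (set by subtype in the subtype rows), stage as a class on both sides, the best k (the matching k in the subtype rows) and 400 replicates (standard error at most 2.5 points).

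| Scenario | Uncut profile | Clusters |
|---|---|---|
| A: 300 markers, 60 shift 0.3 SD per stage, three unrelated background factors | 80-89% | 6-10% |
| A: same, PF slope 0.3 SD per SD | 97-99% | 4-10% |
| B: 50 markers, 10 shift 0.3 SD per stage | 84% | 41% |
| B: 50 markers, 10 shift 0.4 SD, correlation 0.3 | 52% | 20% |
| B: one continuous factor, three settings | 41.2%, 71.3%, 64.2% | 28.5%, 53.2%, 48.7% |
| B: all 50 markers shift 0.2 SD per stage | 100% | 96% |
| B: two true subtypes, k=2 | 69-79% | 78-84% |
| B: three true subtypes, k=3 | 91-95% | 88-98% |

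The one-factor rows lose 12.7, 18.1 and 15.5 points; for PF under one factor the loss was about 15 to 19. With no effect, the full-profile test rejected in 2.5-5% of runs.

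**5. What the planned single-marker models do in the first row A scenario.** If background factors leave the marker SD at 1, noncentrality is 0.3 × √(0.6875 × 90) = 2.36, power 66%, so about 39 of the 60 true markers are flagged. If three factors with loading SD 0.4 raise the SD to √(1 + 3 × 0.16) = 1.22, power is 49% and about 30 are flagged. Add 240 × 0.05 = 12 false ones: 42 to 51 in total, against 300 × 0.05 = 15 by chance.

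**The case against.** The strongest reply is that nothing continuous is lost from the plan. Every marker is tested on its full scale against ordered stage and continuous pulmonary function, and clustering comes on top. A reader might infer that the study would report no promising stage or lung-function signature. Step 5 shows otherwise: in a scenario where clusters almost always fail, the single-marker models flag about three times the number expected by chance. This stands and limits the consequence.

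A reader might also infer that clustering always loses a fixed minimum of power, or discards most of the information. The documents fix neither effect sizes nor correlation structure, and the results range from a loss of many tens of points to a gain of up to about 9. An optimal cut of one axis keeps 64-88% of its variance. Finding groups of patients is a legitimate question in its own right, and where true groups exist clustering does about as well or slightly better. This stands too.

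The lung-function cluster route is explicit only in the conditional sentence, so the point is weaker there than for stage.

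Two further objections count as costs rather than as reasons to do nothing: a global test does not identify the driving markers, and it adds many exploratory tests. The exploratory label does not remove the point, because a screen for signals should be sensitive to graded ones, and the documents give no evidence that discrete subtypes exist.

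**Conclusion.** The point holds in a limited form. Section 6.3 specifies no association between the uncut multi-marker profile and stage or pulmonary function; the specified multi-marker route runs through clusters and, for stage, an unordered table. If the relation is graded, the assumed scenarios at n=90 give losses of about 13 to 30 points for a one-axis signature and far larger ones for a signal spread over many markers amid unrelated variation. The loss is small when all markers shift, and may reverse with true subtypes.

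The size depends on assumed stage mix, effects, correlation and k, so no single figure should be quoted as the loss. The effect is a weak signature-level answer to objectives 2.2.2 and 2.2.3. The single-marker results and the primary feasibility objective are untouched.

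**What to change.** In Section 6.3, keep the clustering as an exploratory description of patient groups and add beside it:

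- a distance-based permutation test (PERMANOVA or distance-based redundancy analysis) of the uncut profile on ordinal LC stage and, separately, on continuous pulmonary function, for pre-surgery, post-surgery and change profiles;
- Euclidean distance for normalised metabolites and for change profiles, and Bray-Curtis for microbial abundances;
- an exploratory label, a report of the number of tests run, and a statement that the result is read with the single-marker models;
- a sentence that no association with cluster membership will not be read as absence of a stage or pulmonary-function signature.

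The cost is a few sentences and a modest amount of analysis, with no new patients, samples or assays. Section 4.2.2 specifies distances for microbiome data only, so metabolite distances must be added. Counting seven metabolite sets (breath volatiles, plus saliva, serum and urine on two platforms) and two to four microbial sets (blood and saliva, taxonomic with or without functional), three profile types and two outcomes give (7+2)×3×2 = 54 to (7+4)×3×2 = 66 tests. The global result shows that a profile is related to stage or lung function, not which markers drive it.
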